		
Page 24, Potential risks: Equalized denominators of rates of AEs by revising to “in approximately twenty people in a population of 10,000 who wear soft contact lenses on an extended wear basis”.
 
Page 25, Potential risks: Added “In rare situations, some individuals may experience vaso-vagal syncope (or similar symptoms) with the use of topical anesthetic or ocular examination procedures”
 
Page 25, Potential risks: Reference to “An examination of the front part of their eyes” has been removed as a benefit to the participant.
	
1.3	[name]	
Page 10-11, study group inclusion criteria description: changed to DD CL wear for the past (minimum) 6 months and CL wear in the same material category in the past (minimum) 3 years. Removed maximum of 7 years CL wear experience. Added no previous history of PMMA CL wear.
 
Page 14-15, study inclusion criteria: revised to reflect the above-mentioned changes in the inclusion criteria.
	29Nov2018
1.4	[name]	Changed the study design to multi-site and reflected this minor change throughout the protocol.	12Jul2019
1.5	[name]	
Section 4.8.1. Added CE marking in Table 1.
 
Section 4.9.3. Changed ‘required to remain within CORE’s premises’, to “required to remain in the study site”.
 
Section 7. Changed “UW SOP012” to “Adverse Event Standard Operating Procedures (SOP) document for the relevant study site”. Typo (Appendix 16) has been removed from the end of the sentence.
 
Section 10. Clarified that Eurolens Research will follow their local standard procedures and forms for study completion and any required feedback to participants.
	04Oct2019

Version #	Originator/s	Description of change(s)	Date
		
Section 12.5. Added retention period of 20 years for Eurolens Research.
 
Section 15.1.3. Provided clarification that Eurolens Research study site will follow their local ethics committee requirements for reporting protocol deviations to the respective ethics committee.
	
1.6	[name]	
Section 4.8.3. Typo corrected from 4.7.6. to 4.8.6.
 
Section 4.8.5. Clarification provided for ordering consumables.
 
Corrected name of “Eurolens Research” site throughout the protocol.
 
Section 8. Clarified reimbursement rate as “\$20 per hour in CORE and it will be based on the rate approved by the respective ethics committee for Eurolens Research study site.
 
Section 10. Added participant remuneration provided by Eurolens Research will be based on the amount approved by the respective ethics committee.
 
Section 12.1. Re study updates, changed to “regular study updates from each site to the sponsor” instead of “regular study updates from CORE to the sponsor”
	08Oct2019
1.7	[name]	
4.1.1 Clarified that trial fitting of study lenses is done in day 1.
 
Section 4.6: Clarified that Eurolens Research may use a different terminology for the ICL (for example, ICF or PIS).
 
Section 4.7.2: Replaced “CORE” with “study site in exclusion criterion#2”
 
Section 8: added flat fees for participant discontinuation at Eurolens.
 
Section 4.9.2: Changed the order of subjective and objective redness measurements.
	10Oct2019

Version #	Originator/s	Description of change(s)	Date
		Section 4.9.2: Clarified that trial fitting of the study lens (randomized eye) will be conducted in groups 1 and 2 (CI wearers) only.	
1.8	[name]	
Section 4.1.1. Study visits: Clarified washout period of at least 1 day (24 hours) before to the 2nd study day and that the second study day should occur within maximum of 30 days from the first study day
 
Section 4.9.3. Study Day 2: Clarified washout period of at least 1 day before the 2nd study day and that the second study day should occur within maximum of 30 days from the first study day.
 
Section 4.10. Moved CL fitting to after confocal microscopy in the summary of procedures for clarification.
	02Mar2020

1 INTRODUCTION & BACKGROUND

Current contact lenses are available in either silicone hydrogel (SH) or hydrogel (H) materials. Silicone hydrogel lenses are far more transmissible to oxygen (they have higher Dk/t) and this is believed to be beneficial for maintaining healthy corneal metabolism. Several publications highlight this by showing less redness around the cornea (less limbal redness with SH compared to H) and the eye in general (less bulbar redness with SH compared to H). ¹⁻³ The severity of corneal infections has also been reported to be reduced with SH lenses compared to H lenses. ^{4, 5}

Napping and sleeping in contact lenses has been reported as a common occurrence.^{6, 7} It is known that, even with no contact lens wear, the limbus may become redder and the cornea swells when the eye is closed ^{8, 9} due to the uptake of water as a result of anaerobic corneal metabolism with eye closure, and deswells upon eye opening. It is of interest to understand whether habitual wear of hydrogel contact lenses modifies this redness and/or the swelling or deswelling response due to the lower level of oxygen through the lens during habitual lens wear.

This non-dispensing, randomised study is designed to evaluate differences in ocular physiological responses to a 3-hour period of monocular closed eye lens wear of a low Dk/t hydrogel (HEMA) lens, between habitual Daily Disposable Silicone Hydrogel (DDSH) lens wearers and habitual Daily Disposable Hydrogel (DDH) lens wearers.

Daily disposable wearers will be used because this replacement modality is being fit more often than re-useable lenses in many countries around the world. A 3-hour period has been chosen in this study because this length of time is anticipated to be sufficient to induce limbal redness and will induce a sufficient corneal swelling response to measure a change in corneal thickness from baseline,^{10, 11} meaning that we do not require the participants to wear the lenses overnight. The reduction in redness and deswelling of the cornea will be followed for 3-hours. This should be sufficient time for the average corneal thickness to return to levels that are very close to baseline values.¹² Limbal redness and corneal thickness will fully recover to baseline values and there will be no permanent changes as a result of this study.¹²⁻¹⁵

2 OBJECTIVES

The primary objectives of this study are:

To compare baseline data between 3 groups - *habitual wearers of DDSH / habitual wearers of DDH / non-lens wearers* - in terms of:

- Limbal & bulbar redness

- Corneal vessel ingrowth

And to compare data post closed eye lens wear in 2 groups - *habitual wearers of DDSH / habitual wearers of DDH* - in terms of:

- Limbal & bulbar redness

The primary study measures are:

- Limbal & bulbar redness (Oculus Keratograph 5)
- Corneal vessel ingrowth (slit-lamp photography & image analysis)

3 HYPOTHESIS

The study main hypotheses are:

- 1) There will be greater corneal vessel ingrowth in habitual wearers of DDH than DDSH and non-lens wearers at baseline.
- 2) There will be greater limbal & bulbar hyperemia response following 3 hours of wearing a low Dk HEMA CL in habitual wearers of DDH than DDSH and non-lens wearers.

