4.10 SUMMARY OF STUDY PROCEDURES

Table 3 summarizes the visits and procedures for the study.

Table 3: Summary of visits and procedures for the study.

	Day 1 Attend V0 after 6-8 hrs of waking	Day 2 Attend V1 at 3 ± 0.5 hours after waking and eye opening in the morning, and wearing habitual spectacles.						
	V0 Screen & Observational data collection	V1 Baseline & CL insertion	V2 Immediately after CL removal	V3 0.5 hr after CL removal	V4 1hr after CL removal	V5 2hr after CL removal	V6 3hr after CL removal	V- Exit
Consent process	x							
CL history and wear schedule	x	x						
Health & medication	x	x						
Permission for CL History from eye care practitioner	x							
Habitual contact lens removal	x							
	x							

	Day 1 Attend V0 after 6-8 hrs of waking	Day 2 Attend V1 at 3 ± 0.5 hours after waking and eye opening in the morning, and wearing habitual spectacles.							
	V0 Screen & Observational data collection	V1 Baseline & CL insertion	V2 Immediately after CL removal	V3 0.5 hr after CL removal	V4 1hr after CL removal	V5 2hr after CL removal	V6 3hr after CL removal	V- Exit	
		■	■	■	■			■	
		x							
Slit lamp biomicroscopy (with staining)	x								
		■							
		■							
		■							
		■							
		■							
		■							
		■							
		■							
		x							
Exit Slit lamp (with staining)	x								x
		■							
		x							

* Additional lenses may be dispensed at scheduled or U/S visits if there is lens defect, or lens damage.

** Not required if visit concurrent with previous one.

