11 STATISTICAL ANALYSIS AND DATA MANAGEMENT

11.1 SAMPLE SIZE CALCULATION

Two previous studies ^{10, 11} assessed differences in corneal response to 3-hour closed eye CL wear between low Dk/t HEMA and PMMA lenses in a group of neophytes. However, there is no

data from similar methodology and participant groups on which to calculate the sample size in the current study. A guide to the minimum sample size for Visit 2 bulbar and limbal hyperemia measures has been calculated from hyperemia data reported in a recent publication reporting objective bulbar and limbal hyperemia (using Oculus Keratograph) while wearing DDH contact lenses in habitual silicone hydrogel lens wearers.¹⁶ This data indicates that to detect an effect size of 1.2 (or 0.5 grade difference) in either bulbar or limbal hyperemia with power of 0.9 and alpha level 0.05, a minimum total sample size of 32 participants should be studied for the 2 study groups in Day 2 (Figure 1).

[figure not shown]
In this initial study to evaluate the response differences between groups it is proposed that 17 participants in each group (shown in randomized side of the graph) are studied to evaluate the size of the differences in bulbar and limbal hyperemia between groups found following lens removal and across the recovery period at each time point. If the data shows a trend of finding a difference between groups, this data can be used to plan a larger study which is powered

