11.2 STATISTICAL ANALYSIS

All data will be analyzed by CORE at the University of Waterloo. Data analysis will be conducted using Statistica, SPSS or SAS. Descriptive statistics will be provided on information regarding baseline variables (age, gender, refractive error distribution, etc.). Analysis of variables will be conducted separately on each eye, and data will not be pooled. For assessments conducted for each eye separately, the right eye will be used for analysis if there is no difference between

eyes. If a general difference is found (e.g. for paired t-test / Wilcoxon matched pairs) between OD and OS, a comment will be provided.

The critical alpha level for statistical significance will be set at $p \leq 0.05$, with no adjustments for multiple comparisons.

All participants who were evaluated and complete all scheduled study visits will be included in the analysis cohort. In the event of missing data, individual data points will be excluded from the analysis and not extrapolated from the collected data.

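### Hypothesis 2 is about the redness response to study-lens wear, but the visible plan compares post-lens levels only, gives the Visit 1 value no role, and names a group that never wears the lens

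*Combined protocol and SAP*

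**What the plan says.** Hypothesis 2 in Section 3 predicts a greater limbal and bulbar "hyperemia response following 3 hours of wearing a low Dk HEMA CL in habitual wearers of DDH than DDSH and non-lens wearers".

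The matching objective in Section 2 is narrower: "And to compare data post closed eye lens wear in 2 groups", namely habitual wearers of daily disposable silicone hydrogel (DDSH) and hydrogel (DDH) lenses. Baseline redness is a separate three-group objective and is not linked to the post-lens comparison.

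Section 11.1 gives a guide to the "minimum sample size for Visit 2 bulbar and limbal hyperemia measures" and plans group differences after lens removal and at each recovery time point. It adds that "this data can be used to plan a larger study".

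Section 11.2 names no change score, covariate or model for redness. Baseline appears there only in this form: "Descriptive statistics will be provided on information regarding baseline variables".

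Two places hint that Visit 1 is the natural reference. Table 3 (Section 4.10) heads that column "V1 Baseline & CL insertion", and Section 1 says "Limbal redness and corneal thickness will fully recover to baseline values". Neither is an analysis rule.

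Section 1 also cites publications reporting "less limbal redness with SH compared to H) and the eye in general (less bulbar redness with SH compared to H". Sections 4.1.1, 4.7.1 and 4.9.3 limit Day 2 to Groups 1 and 2; Group 3 attends the first visit only and is not exposed to the study lens.

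**The concern.** A response is what the lens-wear period does to the eye. A Visit 2 level mixes that with whatever redness was present before the lens went in. Only the eye is randomised. Habitual lens type is self-selected, and matching covers age, ethnicity and lens power, not redness. The protocol's own background gives a reason to expect DDH wearers to be redder in habitual wear, and part of that may remain after the lens-free day.

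One analyst could test the Visit 2 level, another the change from Visit 1, another Visit 2 adjusted for Visit 1, and all would comply with the plan. A raw comparison answers the Section 2 objective (a difference in level) but not Hypothesis 2. A pre-existing gap read as response could also enter the effect size for the larger study that Section 11.1 foresees.

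The non-lens-wearer clause is a plain inconsistency: a main hypothesis contains a contrast for which no data will exist.

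**Working it through.** **Inputs from the documents.** Effect size 1.2, equated with 0.5 grade; power 0.9; alpha 0.05; 32 in total for two groups (Section 11.1). Target of 17 completers per group (Section 4.7.1). Significance at p≤0.05 (Section 11.2).

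**Assumptions, because the documents give no figure.** Visit 1 gap g of 0.10 to 0.25 grade; pre/post correlation ρ of 0 to 0.8; equal SD at Visits 1 and 2; two-sided testing.

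**1. The plan's own figure.** Two-sample t test, noncentrality d√(n/2), 2n−2 degrees of freedom.
- 16 per group: 1.2 × √8 = 3.39, power 0.907.
- 15 per group: power 0.887.

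The minimum is 16 per group, or 32 in total, as stated. At 17 per group power is 0.924. The number is right for a post-only comparison.

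**2. Implied SD.** 0.5/1.2 = 0.417 grade.

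**3. Equal change in both groups, Visit 1 gap g persisting in full.** The raw Visit 2 test has noncentrality (g/0.417) × √(17/2).

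| g (grade) | noncentrality | raw Visit 2, p≤0.05 |
|---|---|---|
| 0.10 | 0.24 × 2.915 = 0.70 | 10% |
| 0.20 | 0.48 × 2.915 = 1.40 | 27% |
| 0.25 | 0.60 × 2.915 = 1.75 | 40% |

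Change from Visit 1 removes the gap exactly, so its rate stays at 5%. ANCOVA leaves an expected difference of (1−ρ)g. For g = 0.20 that is 0.14, 0.10 and 0.04 grade at ρ = 0.3, 0.5 and 0.8. Simulation (100,000 trials per cell) gives p≤0.05 in 16%, 12% and 7%.

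**4. If the gap does not fully persist.** Let c be the fraction of the gap still present at Visit 2 for reasons other than the lens. The expected group differences are c·g (raw), (c−1)·g (change) and (c−ρ)·g (ANCOVA). With c = 0, g = 0.20 and ρ = 0.8, ANCOVA shows −0.8 × 0.20 = −0.16 grade, with p≤0.05 in 41% of trials. Change shows −0.20 grade.

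**5. Power for 0.5 grade at 17 per group, no Visit 1 gap.** The SD of change is 0.417 × √(2(1−ρ)). ANCOVA figures are simulated.

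| ρ | raw | SD of change | change | ANCOVA |
|---|---|---|---|---|
| 0 | 0.92 | 0.589 | 0.67 | 0.91 |
| 0.3 | 0.92 | 0.493 | 0.82 | 0.94 |
| 0.5 | 0.92 | 0.417 | 0.92 | 0.97 |

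If a 0.20 gap fades completely, ANCOVA power is 0.85 at ρ = 0.3 or 0.5.

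**6. Group 3.** The number with post-lens data is 0, so the contrast between DDH and non-lens wearers in Hypothesis 2 cannot be computed.

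**The case against.** The strongest reply is that the stated objective is a post-wear comparison of levels in an initial study, which raw Visit 2 data answer. On that view only one word in a hypothesis is loose. Section 11.2 is brief for every endpoint, and Visit 1 follows a lens-free day with participants in spectacles, so little of the habitual difference may remain. At a 0.10 grade gap the raw rate is only 10%. The Group 3 clause is a drafting slip that would not lead anyone to run a wrong analysis on Day 2.

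Much of this stands. The gap is assumed, and the cited background does not describe redness after a lens-free day. A reader might infer that the trial has a 27% false-positive rate. The documents do not support that: the figure depends on an assumed gap that persists in full, and Section 11.2 does not commit to any particular test.

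A reader might also infer that ANCOVA is the safe answer in all cases. It is not. In non-randomised groups, ANCOVA and change answer different questions when a Visit 1 gap exists. ANCOVA removes only part of a gap that persists, and over-corrects one that fades when the correlation is high. If a gap fades, the groups really do differ in change, so whether a significant change score is an error depends on how response is defined.

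Nor can one infer that redness is not measured at Visit 1. The Visit 1 procedures in Sections 4.1.1, 4.9.3 and 4.10 are largely redacted.

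What the reply does not remove is that a main hypothesis concerns a response, its reference value is undefined, and one of its contrasts has no data.

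**Conclusion.** The point holds in two parts. First, the visible plan does not test Hypothesis 2 as a response: the comparisons it describes are of post-lens levels in non-randomised groups, with no analytic role for Visit 1. The possible distortion runs from none, if no gap remains at Visit 1, to the 10–40% rates above for a gap of 0.10–0.25 grade that fully persists. Those rates rest on the assumed gap, equal SDs and the SD implied by Section 11.1. Second, the non-lens-wearer contrast in Hypothesis 2 is untestable and conflicts with the two-group objective in Section 2; this needs no assumption.

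The issue is the definition of the comparison, not the sample size. It should be fixed before analysis. Confidence is moderate, because the Visit 1 procedures cannot be seen and Section 11.1 breaks off mid-sentence in the available text.

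**What to change.** 1. In Section 3, delete non-lens wearers from Hypothesis 2, or limit that contrast to Day 1 redness, which Section 2 already covers.
2. In Section 11.2, state that response is judged against the lens-wearing eye's Visit 1 value. Compare DDH and DDSH on Visit 2 redness by ANCOVA with Visit 1 as covariate. Report change from Visit 1 and the Visit 1 group means alongside, and treat the recovery time points the same way.
3. Keep the raw Visit 2 comparison for the Section 2 objective, labelled as a comparison of levels.
4. Do not use Visit 0 as the reference. It takes place 6–8 hours after waking with habitual lenses worn that day; Visit 1 takes place 3 ± 0.5 hours after waking, in spectacles, after a lens-free day.
5. State the limits: ANCOVA and change can disagree when a Visit 1 gap exists, neither is best in every case, and change has power below 0.90 for 0.5 grade when the correlation is clearly under 0.5.

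The cost is wording and a little analysis. With no Visit 1 gap, ANCOVA keeps power of about 0.91 or more at 17 per group, so no participants need be added. This assumes redness is recorded at Visit 1; if it is not, one redness measurement before lens insertion is needed.

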4 MATERIALS AND METHODS

4.1 STUDY DESIGN

4.1.1 OVERALL DESIGN

This study is a multi-site, prospective, randomized, non-masked, unilateral, non-dispensing study. The first part of the study (Day 1) involves collecting measures from three groups of participants (see group descriptions below). The second part (Day 2) only involves the two contact lens wearing groups (Group 1 & Group 2) and involves comparing between habitual wearers of DDSH and DDH for corneal swelling response & recovery following wearing a low Dk HEMA CL in a randomized eye under eye closure conditions for 3 hours. The contralateral control eyes with no lens wear will remain open during the test period.

Study Group inclusion criteria description:

The following 3 groups with age (within \pm 5 years), ethnicity (being Asian vs. non-Asian, this is due to possible differences in physiological response to corneal hypoxia in Asian and non-Asian participants), and spherical contact lens power (within \pm 2.00D) matched will be involved in this study:

GROUP 1: For the past (minimum) 6 months has ONLY worn spherical DDSH lenses AND prior to wearing this lens they only wore SH material lenses in the past (minimum) 3 total years.

GROUP 2: For the past (minimum) 6 months has ONLY worn spherical DDH lenses AND prior to wearing this lens they only wore H material lenses in the past (minimum) 3 total years.

GROUP 3: No previous experience of contact lens wear (no need to match Rx of this group).

Additional criteria:

For groups 1 & 2, currently and for at least the previous 6 months has had habitual daily disposable wear schedule of at least 8 hrs a day, 5 days a week in only one material category - either silicone hydrogel or hydrogel material.

For groups 1 & 2, no previous history of overnight wear or PMMA (polymethylmethacrylate) lens wear.

For groups 1 & 2, a minimum of 3 years of lens wear experience.

For group 3, no previous history of contact lens wear.

Study visits:

It is anticipated that this study will involve 2 days with at least 1 day in-between with no lens wear and no use of any rewetting drops (if applicable) as the washout period. The second study day should occur within maximum of 30 days from the first study day. The required minimum study washout period will be at least 1 day of no lens wear and no use of any rewetting drops (if applicable) on the day (24 hours) before the second study day. This study has up to a total of 7 scheduled visits:

Study Day 1

The first study day will be observational in nature for collecting comparison data across all 3 participant groups described above. There will be only one study visit on day 1.

Visit 0: This visit includes screening, confirmation of CL history, measurements of [REDACTED]

[REDACTED], slit-lamp biomicroscopy, [REDACTED]

[REDACTED]

[REDACTED] Then Day1 exit slit-lamp biomicroscopy [REDACTED]

[REDACTED]

Study Day 2

Only the study groups 1 & 2 will be involved in the second day of study. They will attend the study visit 1 on day 2 at 3 ± 0.5 hours after waking and eye opening in the morning, and wearing their habitual spectacles.

[REDACTED]
[REDACTED]
[REDACTED] [REDACTED]
[REDACTED]
[REDACTED]
[REDACTED]

Visit 2:

[REDACTED]
[REDACTED]
[REDACTED]
[REDACTED] [REDACTED]
[REDACTED]
[REDACTED]
[REDACTED]

Visit 4: 1hr after CL removal

[REDACTED] [REDACTED]
[REDACTED]
[REDACTED]
[REDACTED]

Visit 6: 3hr after CL removal

[REDACTED] the objective ocular
redness measurement OU [REDACTED]

Exit Visit:

[REDACTED]

Biomicroscopy including corneal staining, OU

Study exit [REDACTED]

Exit the study.

4.1.2 RANDOMIZATION

A randomization schedule will be generated using SAS or a web-based program: (www.randomization.com). The final study randomization schedule will be generated by CORE's Data Management Team, and provided to the research assistants and clinical investigators at each study site for use during the study.

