4.1.3 MASKING

There will be no masking in this study. Masking of the Study investigators is not possible as they need to measure the study main variables in the predetermined randomized eye.

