4.7.2 INCLUSION AND EXCLUSION CRITERIA

A person is eligible for inclusion in the study if he/she:

1. Is between 17 and 60 years of age inclusive (age matching required between all 3 study groups), and has full legal capacity to volunteer;
2. Has had a self-reported oculo-visual examination in the last two years.
3. Has read and signed an information consent letter;
4. Is willing and able to follow instructions and maintain the appointment schedule;

5. No previous history of overnight contact lens wear or PMMA (polymethylmethacrylate) lens wear.
6. Auto-refraction vertexed spherical equivalent between +4.00 and -8.00 (prescription matching required between groups 1 & 2). This criterion is non-applicable to participants in group 3.
7. Is found to be in one of the study groups matched by age (± 5 years), ethnicity (Asian vs. non-Asian) and CL Rx (± 2.00 D) according using the following criteria:

GROUP 1: For the past (minimum) 6 months has ONLY worn spherical DDSH lenses AND prior to wearing this lens they only wore SH material lenses in the past (minimum) 3 total years.

GROUP 2: For the past (minimum) 6 months has ONLY worn spherical DDH lenses AND prior to wearing this lens they only wore H material lenses in the past (minimum) 3 total years.

GROUP 3: No previous experience of contact lens wear (no need to match Rx of this group).

8. For groups 1 & 2, currently and for at least the previous 6 months has had habitual daily disposable wear schedule of at least 8 hrs a day, 5 days a week in only one material category - either silicone hydrogel or hydrogel material. This criterion is not-applicable to participants in group 3.
9. Is willing to wear the study contact lens in the randomized eye for 3 hours of eye closure on the second study day. This criterion is not-applicable to participants in group 3.
10. Has clear and healthy corneas and anterior eye and no active* ocular disease;
11. Can achieve monocular HCVA of logMAR 0.10 or better in each eye with subjective refraction or pinhole.
12. Can achieve acceptable fit and comfort in the randomized eye with the study lens. This criterion will be confirmed at the baseline visit (V1). This criterion is not-applicable to participants in group 3.
13. Has a wearable pair of spectacles.

A person will be excluded from the study if he/she:

1. Is participating in any concurrent clinical trial;
2. Is unable/unwilling to provide permission for the study site to seek CL history from their eye care practitioner

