4.8.4 CONTACT LENS FIT AND WEAR

This is not a dispensing study. The fit of study contact lens will be evaluated on the randomly determined study eye during the baseline visit (Visit 1, Study Day 2) to ensure acceptable lens parameters and fit. After placing the study lens on the randomized eye, slit lamp examination will be conducted to confirm acceptable lens fit and comfort, and the absence of debris underneath the lens. Only participants with acceptable lens fit and comfort in the randomized eye will be eligible to continue in the study. The study lens will then remain on that eye for 3-hours and the eye will be lightly covered to keep it completely closed. Complete eye closure will be attained through the use of gauze and surgical tape, covered by a loosely-fitting ophthalmic eye patch which does not create excess pressure on the eye. The contralateral (no-lens) eye will remain open during the 3 hour period.

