4.9 SCHEDULED AND UNSCHEDULED VISITS

4.9.2 STUDY DAY 1 (VISIT 0)

The first study day will be observational in nature for collecting comparison data across all 3 participant groups described above. There will be only one study visit (visit 0) in day 1.

Visit 0 (2.75 hours): This visit includes screening, confirmation of CL history, measurements of [REDACTED] slit-lamp biomicroscopy, [REDACTED]
[REDACTED]
[REDACTED]

At the screening, all participants who sign the informed consent letter will be assigned a study ID number. The investigator will determine participant eligibility using the inclusion and exclusion criteria. Ineligible participants will be discontinued from the study. The procedures to be performed in visit 0 are outlined below:

- The participant is expected to attend the screening visit 6-8 hours after waking. The participants in groups 1 and 2 (CL wearers) will attend, having inserted their CLs 0.5 hours after waking that day. Participants in group 3 will attend this visit with habitual spectacles, if any.
- The participant will be required to read and sign an Informed Consent Form [REDACTED] prior to enrollment. When the participant has signed the consent form, the participant will be considered to be enrolled in the study.
- Participant demographics and medical history (age, sex, medical conditions, medications, allergies).
- Contact lens history (habitual lens information and wearing habits) (N/A in group 3).
- Participants will be asked to review and sign a permission request to seek CL history from their eye care practitioner.
- Contact lens removal (N/A in group 3).
- [REDACTED]
- [REDACTED] n Slit lamp biomicroscopy.
- [REDACTED]
[REDACTED]
- Slit lamp biomicroscopy [REDACTED]
[REDACTED]
- Confirmation of study eligibility and continuation
- [REDACTED]
[REDACTED]
- [REDACTED]

- [REDACTED]
- [REDACTED]
- [REDACTED]
- [REDACTED]
- [REDACTED]
- [REDACTED]
- Day1 exit Slit lamp biomicroscopy assessments including corneal & conjunctival staining (safety measure).
- [REDACTED]

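### Section 4.1.2 hands the full eye-randomisation schedule to unmasked site staff, so the test eye can be known before eligibility is decided; the likely effect on the DDH versus DDSH comparison is small and the remedy is cheap

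*Combined protocol and SAP*

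**What the plan says.** Section 4.1.2 separates generation of the schedule from the clinic: "The final study randomization schedule will be generated by CORE's Data Management Team". It then ends that separation, because the schedule is "provided to the research assistants and clinical investigators at each study site for use during the study". Section 4.1.3 states "There will be no masking in this study" and explains that investigators cannot be masked because "they need to measure the study main variables in the predetermined randomized eye".

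On timing, Section 4.9.2 says that at screening "all participants who sign the informed consent letter will be assigned a study ID number". The next sentence reads "The investigator will determine participant eligibility using the inclusion and exclusion criteria". Section 14, in its list of status-report items, defines randomised participants as those given a study ID.

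A second selection step comes on Day 2. Inclusion criterion 12 in Section 4.7.2 requires that the participant "Can achieve acceptable fit and comfort in the randomized eye with the study lens", to be confirmed at Visit 1. Section 4.8.4 adds: "Only participants with acceptable lens fit and comfort in the randomized eye will be eligible to continue in the study".

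No readable section mentions sealed envelopes, release of one assignment at a time, or release only after eligibility has been confirmed.

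**The concern.** Generating a random list protects a comparison only if nobody who decides on entry can see the next assignment. Here the list goes to staff in the same roles that screen participants. The stated reason for not masking concerns measurement after assignment; it is no reason to disclose the assignment before eligibility is settled.

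What is at stake is selective exclusion. A participant whose assigned eye looks unpromising could be screened out, or failed on fit or comfort, when the same person assigned the other eye would have been kept. Section 11.2 limits the analysis cohort to participants who complete all scheduled visits, so such exclusions would not show in the results. Exposed eyes could then start out systematically different from control eyes. If this happened in one habitual-lens group and not the other (and staff know the group), it would carry into the Day 2 post-lens comparison.

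**Working it through.** **1. Order of events.** Consent and study ID come first (4.9.2), and having an ID counts as being randomised (14). Habitual lens removal, slit-lamp examination and confirmation of eligibility come later in the Visit 0 list. Site staff hold the schedule (4.1.2). If the schedule is keyed to ID, the eye is knowable when eligibility is decided. At Visit 1 the eye has to be known, since fit is judged on it.

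**2. The plan's own figure.** Section 11.1 gives effect size 1.2 (0.5 grade), power 0.9, alpha 0.05 and a minimum total of 32. An exact two-sided two-sample t calculation gives 16 per group, total 32, power 0.907, so the figure reproduces. At the target of 17 per group the power is 0.924. Concealment changes none of these numbers. The implied SD is 0.5/1.2 = 0.417 grade.

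**3. Size of a between-eye difference.** The documents give no between-eye correlation r, so I assume 0.7 to 0.9. For bivariate normal eyes, mean |OD − OS| = 2 × SD × √((1 − r)/π):
- r = 0.7: 0.833 × √(0.3/π) = 0.258 grade
- r = 0.8: 0.833 × √(0.2/π) = 0.210 grade
- r = 0.9: 0.833 × √(0.1/π) = 0.149 grade

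**4. Shift from steering.** Suppose a fraction f of participants end up with the lens on the less red eye and the rest are assigned at random. The exposed-minus-control difference before the lens goes on moves by f × mean |OD − OS|. The exposed-eye level moves by half of that, and this half is what enters the DDH versus DDSH comparison if only one group is steered. The values of f are illustrative. The last column is a two-sided two-sample t-test with 17 per group and SD 0.417.

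| f | r | Exposed − control shift (grade) | Group-comparison shift (grade) | Share of 0.5 grade | False-positive rate |
|---|---|---|---|---|---|
| 0 | any | 0 | 0 | 0% | 5.0% |
| 0.25 | 0.9 | 0.037 | 0.019 | 4% | 5.2% |
| 0.25 | 0.7 | 0.064 | 0.032 | 6% | 5.6% |
| 0.50 | 0.9 | 0.074 | 0.037 | 7% | 5.7% |
| 0.50 | 0.7 | 0.129 | 0.064 | 13% | 7.2% |

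If both groups are steered alike, the shift in the group comparison cancels.

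**5. The exposed-versus-control contrast.** A paired t-test of the two eyes before lens insertion in 34 wearers (2 × 17), simulated with 20,000 replicates, rejects about 22% of the time at f = 0.25 and about 69% at f = 0.50, against 5% with no steering.

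**6. How much exclusion this would take.** If steering works only by rejecting a fraction q of participants whose redder eye was assigned, then f = q/(2 − q), so q = 2f/(1 + f).
- f = 0.25: q = 0.5/1.25 = 40% of those assignments, or 20% of all eligible wearers. Completing 17 needs 17/0.80 = 21.25 per group.
- f = 0.50: q = 1/1.5 = 67%, or one third of all. Completing 17 needs 17/(2/3) = 25.5 per group.

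The cap in Section 4.7.1 is 26 per group, so 50% steering would use essentially the whole allowance and leave nothing for ordinary dropout.

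**The case against.** The strongest reply is that the comparison most at risk is not one the plan makes. Sections 2 and 3 list between-group comparisons only. Section 11.2 analyses eyes separately, and its paired test is right against left, not exposed against control. A reader might take the 22% and 69% in step 5 as the trial's inflated error rate. The documents do not support that: Section 4.1.1 calls the fellow eye a control, but no listed objective or hypothesis tests exposed against control eyes. This stands.

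A reader might also infer that staff could pick the order of IDs, or use a repeat screening, to obtain a preferred eye. Both are weak routes. The ID is given at consent, before the eye examinations in the Visit 0 list, each participant has one unique ID, and nothing says that a repeat screening brings a new assignment. Selective exclusion is the route that remains, and step 6 shows that heavy use of it would strain the enrolment cap.

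Three further points stand in part:
- The schedule's format is not stated, visit steps are redacted, and the documents name roles, not individuals. That the same people hold the list and judge eligibility and fit, and that every assignment is openly visible, is therefore inference. An unstated concealment step cannot be ruled out.
- Redness is measured by instrument. If the response is analysed as change from the Visit 1 baseline, a shift in starting level would largely drop out.
- Concealment cannot protect the criterion 12 decision, because the lens has to be on the assigned eye.

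None of this supplies a reason to release the whole schedule to the sites.

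**Conclusion.** The point holds as a weakness in how the eye allocation is implemented, worth correcting but with limited consequences. Section 4.1.2 states that unmasked site staff receive the schedule, and the ID that counts as randomisation precedes the eligibility decision. If the schedule is keyed to ID, selective exclusion by assigned eye is possible.

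It would be tempting to conclude that the DDH and DDSH groups themselves are compromised. They are not: lens history sets group membership, so concealment has no bearing on it.

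The planned post-lens group comparison would move by roughly 0.02 to 0.06 grade, with a false-positive rate of 5.2% to 7.2%. That rests on one-sided steering at 25% to 50%, an assumed between-eye correlation of 0.7 to 0.9, and the SD implied by Section 11.1. Nothing in the documents suggests that steering is intended or expected. Any later analysis of exposed against control eyes would be considerably more vulnerable.

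**What to change.** In Section 4.1.2, replace the distribution of the schedule to site staff with text to this effect:
- CORE's Data Management Team holds the schedule and does not release it to the sites.
- Each participant's eye is released individually by study ID, by email or sequentially numbered sealed envelope, no earlier than the Visit 0 step that confirms eligibility and continuation. Where Visit 1 pre-lens measures are taken on both eyes, release follows those measures.
- An assignment is not reused if the participant leaves.

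Add to Section 11.2 that exclusions under criterion 12 (fit and comfort) will be reported by group and assigned eye. The eye has to be known for that decision, so reporting is the available safeguard.

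Separate blocked sequences by group and site are not needed for this purpose. They address balance, not concealment, and would make four strata for about 34 wearers when one site may enrol none.

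The cost is one email or envelope per participant from a team that already generates the list. Sample size, power and alpha do not change. If a concealment step already exists, one sentence in 4.1.2 describing it would settle the release question.
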